Safety data are also available from the Week 24 interim analysis (IA) conducted for the Phase 2a JADE study, which was mentioned above. There were no deaths or SAEs considered at least possibly related to the study intervention. Most AEs were grade 1 or 2 in severity. The majority of reported AEs were considered unrelated to JNJ-6379 by the investigator. Adverse events leading to treatment discontinuation were reported in 1 participant on placebo + NA (abdominal discomfort/gastrointestinal upset) and 1 participant on JNJ-6379 75 mg + NA (streptococcal toxic shock syndrome, acute cardiac failure, myocarditis and muscle necrosis). Most frequent grade 3 or 4 AEs were gastrointestinal disorders (colitis and dyspepsia in the placebo + NA arm) and investigations (ALT and ALT elevations in the JNJ-6379 75 mg + NA and JNJ-6379 250 mg + NA arms).

Increased cholesterol is considered a laboratory abnormality of interest for JNJ-6379, based on safety review from nonclinical and clinical studies. Cholesterol increased was reported as an AE in 4 (4.1%) participants on JNJ-6379 for the pooled Phase 1 studies, in 1 (2.4%) participant on JNJ-6379 for the Phase 1 study 56136379HPB1005, and in none of the participants in the Phase 2a JADE study.

Combination of JNJ-3989 and JNJ-6379

Clinical data of triple combination treatment of JNJ-3989, JNJ-6379, and NA are available from the Phase 1/2a AROHBV1001 study (Cohort 12). Twelve adult chronic HBV mono-infected participants have received 3 subcutaneous injections of JNJ-3989 (200 mg Q4W) in combination with oral JNJ-6379 (250 mg QD) and oral NA treatment (ETV or tenofovir disoproxil).

Up to the IA cut-off date of 29 October 2019, no deaths, SAEs, or treatment-emergent adverse events (TEAEs) leading to study drug discontinuation were reported. Two (16.7%) participants reported at least 1 TEAE during the treatment phase. The TEAEs (upper respiratory tract infection and hypertension) were of mild severity and considered not related to the study drug by the investigator.

The triple combination treatment of JNJ-3989, JNJ-6379, and NA is currently being investigated in chronic HBV mono-infected participants in the ongoing Phase 2 clinical studies 73763989HPB2001 (REEF-1, 90 participants in triple combination Arm 1) and 73763989PAHPB2002 (REEF-2, 80 participants in triple combination Arm 1).

Since the initial protocol writing, interim results of the REEF-1 and REEF-2 studies had become available. In the primary REEF-1 analysis (Week 48, end of treatment) the mean reduction of HBsAg levels in the triple arm (JNJ-6379+JNJ-3989 100mg+NA) appeared to be less than in the dual arm (JNJ-3989 100mg+NA). More recent interim results of the REEF-2 study (Week 48, end of treatment) confirmed this observation when the effect of JNJ-6379+JNJ-3989 200mg+NA on mean HBsAg level reduction in REEF-2 study is compared to JNJ-3989 200mg+NA in the REEF-1 study. To match with the REEF-2 population, this cross-study comparison focused on the REEF-1 subpopulation of HBeAg negative, virologically suppressed participants with chronic hepatitis B. PK-PD modelling analyses accounting for variability in baseline characteristics further support this observation. Therefore, a negative effect of JNJ-6379 on the HBsAg lowering effect of JNJ-3989+NA is suspected.

2.2.3.2. Combination of JNJ-3989 and JNJ-6379 with Entecavir, Tenofovir Disoproxil, or Tenofovir Alafenamide

Entecavir monohydrate is an HBV NA reverse transcriptase inhibitor indicated for the treatment of chronic HBV infection in adults and children at least 2 years of age with evidence of active viral replication and either evidence of persistent elevations in serum aminotransferases (ALT or aspartate aminotransferase [AST]) or histologically active disease. The most common adverse reactions ($\geq 3\%$ of participants) are headache, fatigue, dizziness, and nausea.

There is no common target organ between JNJ-6379 or JNJ-3989 and ETV ([Memorandum 2005](#)).

Tenofovir disoproxil (available in several salt forms including tenofovir disoproxil fumarate and tenofovir disoproxil maleate) is a first-generation oral prodrug of the NA tenofovir that is indicated for the treatment of chronic HBV infection in adult and pediatric patients at least 12 years of age. In addition, tenofovir disoproxil in combination with other antiretrovirals is indicated for the treatment of human immunodeficiency virus type 1 (HIV-1) infection in adult and pediatric patients at least 2 years of age. The most common adverse reactions ($\geq 10\%$ of participants) are abdominal pain, nausea, insomnia, pruritus, vomiting, dizziness, and pyrexia.

Tenofovir alafenamide is an ester prodrug of the NA tenofovir that is indicated for the treatment of chronic HBV infection in adults and that is characterized by a better safety profile than tenofovir disoproxil. The most common adverse reaction ($\geq 10\%$ of participants) is headache.

The single common toxicity target organ between JNJ-6379, JNJ-3989, and tenofovir disoproxil or TAF is the kidney (see Section 2.2.2.2, Combination of JNJ-3989 or JNJ-6379 With Entecavir, Tenofovir Disoproxil, or Tenofovir Alafenamide).

Clinical data on dual combination treatment of JNJ-6379 and NA are available from the ongoing Phase 2a 56136379HPB2001 study ([IB JNJ-6379 2021](#)). In participants treated with tenofovir disoproxil, C_{trough} concentrations of tenofovir at Week 12 were higher in participants receiving tenofovir disoproxil in combination with JNJ-6379 than in participants receiving tenofovir disoproxil as monotherapy (94.2 [30.0] and 115 [66.0] ng/mL for 75- and 250-mg JNJ-6379, respectively in combination with tenofovir disoproxil, vs 66.8 [37.0] ng/mL as tenofovir disoproxil monotherapy).

Clinical data of triple combination treatment of JNJ-3989, JNJ-6379, and NA are available from the Phase 1/2a AROHBV1001 study (see Section 2.2.3.1, JNJ-3989 and JNJ-6379). Dosing JNJ-6379 with NA for 12 weeks did not show any clinically relevant changes in kidney parameters/glomerular function.

For further information regarding ETV, tenofovir disoproxil, and TAF, refer to the respective currently approved prescribing information.

Overall Assessment of the Combination Therapy

Based on the points listed below, no clinically relevant DDIs and no specific concerns about additive or synergistic toxicities in the kidney are expected when JNJ-6379 or JNJ-3989 are combined with ETV, or tenofovir disoproxil, or TAF:

- Available toxicology data, described in Section 2.2.2.2, Combination of JNJ-3989 or JNJ-6379 With Entecavir, Tenofovir Disoproxil, or Tenofovir Alafenamide.
- In vitro drug transporters.
- Metabolic interaction data.
- Absence of relevant DDIs in the combination toxicity studies up to 3 months with JNJ-6379 and JNJ-3989.
- Absence of synergistic or additive histology findings in the kidney observed in the combination toxicity studies up to 3 months with JNJ-6379 and JNJ-3989.
- Available clinical data with JNJ-6379 (JADE study [56136379HPB2001]) up to 24 weeks treatment on the absence of changes in kidney parameters/glomerular function.
- Available clinical data of triple combination treatment of JNJ-3989, JNJ-6379, and NA described in Section 2.2.3.1, JNJ-3989 and JNJ-6379.

In addition, pancytopenia in 1 rat and a mild platelet decrease were seen in the combination groups in the 3-month combination toxicity study (preliminary data, Section 2.2.2.1, JNJ-3989 and JNJ-6379). No significant abnormalities of hematologic parameters have been observed in clinical studies to date. The sponsor is implementing additional monitoring of significant on-treatment hematologic changes in clinical studies with dosing longer than 4 weeks (see Section 8.3.6.6, Hematologic Abnormalities). For further information, refer to the latest version of the IBs for JNJ-3989 and JNJ-6379 ([IB JNJ-3989 2020](#); [IB JNJ-6379 2021](#)).

2.2.3.3. Combination of JNJ-3989 and JNJ-6379 with PegIFN- α 2a

PegIFN- α 2a is a covalent conjugate of recombinant alfa-2a interferon that is indicated for the treatment of CHB in adult and pediatric patients at least 3 years of age. In addition, PegIFN- α 2a in combination with other medicinal products is indicated for the treatment of chronic hepatitis C virus (HCV)-infection in adult and pediatric patients at least 5 years of age and not treated before. The most common adverse reactions ($\geq 10\%$ of participants) are anorexia, anxiety, headache, concentration impairment, dyspnea, cough, alopecia, dermatitis, pruritis, dry skin, myalgia, arthralgia, asthenia, pyrexia, and fatigue. For further information regarding PegIFN- α 2a, refer to the currently approved prescribing information.

Treatment with PegIFN- α 2a has been associated with decreases in platelet count (common adverse reaction). In the Phase 1/2a AROHBV1001 study (see Section 2.2.3.1, JNJ-3989 and JNJ-6379), no effect on platelet count has been observed in the triple combination treatment cohort 12 (JNJ-3989, JNJ-6379, and NA). Of the 84 adult chronic HBV-infected participants that received 3 subcutaneous injections of JNJ-3989, 6 participants developed grade 1 platelet reduction with no general trend towards a continuous decline. For JNJ-6379, no effect on platelet count has been observed in ongoing Phase 2a 56136379HPB2001 study (JADE) for the 189 adult chronic HBV-infected participants that were dosed with JNJ-6379.

Based on pre-clinical data, a potential common toxicity target organ between JNJ-6379, JNJ-3989, and PegIFN- α 2a is the bone marrow (see Section 2.2.2, Nonclinical Studies). Bone marrow suppression is a known side effect of PegIFN- α 2a (rare).

No PK interaction is expected between JNJ-3989 or JNJ-6379 and PegIFN- α 2a based on the known pharmacologic profile of the compounds (IB JNJ-3989 2020; IB JNJ-6379 2021; Yeh 2019).

Since initial protocol writing, 2 clinical studies using the combination of JNJ-3989 and PegIFN- α 2a are ongoing: REEF-IT and PENGUIN. Nonclinical studies to investigate the effect on platelet count decreases were completed and results are summarized in Section 2.2.2.3, Combination of JNJ-3989 or JNJ-6379 With PegIFN- α 2a. Up to 48-week hematology data from the ongoing Phase 2 clinical study REEF-1 are available and overall around 5% of the participants experienced AEs or laboratory abnormalities related to hematologic abnormalities, the majority of mild to moderate severity. The hematologic abnormalities resolved on continued JNJ-3989+NA treatment.

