Treatment with JNJ-6379 may lead to emergence of viral variants with reduced susceptibility or resistance to JNJ-6379. Based on nonclinical data, these variants remain susceptible to tenofovir disoproxil and ETV but might affect treatment options with CAMs in the future. All 5 participants with virologic breakthrough in the JADE study who received 75 mg JNJ-6379 monotherapy, had an emerging core amino acid mutation T33N, which is known to confer reduced JNJ-6379 activity in vitro (see Section 2.2.3.1, JNJ-3989 and JNJ-6379, for the results of the IA).

Drug-drug Interactions

Based on results from DDI study 56136379HPB1004 investigating the potential effect of coadministration of JNJ-6379 with oral contraceptives, it is not anticipated that the efficacy of oral contraceptives will be impacted during coadministration with JNJ-6379 since the exposure of a progestin sensitive to CYP3A4 induction was not significantly affected by coadministration of JNJ-6379. In contrast, it is anticipated that coadministration with ethinylestradiol-containing contraceptives will result in an increased exposure to ethinylestradiol. Therefore, specific requirements on the use of ethinylestradiol-containing contraceptives are included in Section 6.5, Concomitant Therapy.

2.3.2.2.3. Potential Risks for Entecavir, Tenofovir Disoproxil, Tenofovir Alafenamide, and PegIFN- α 2a

For the general potential risks of ETV, tenofovir disoproxil, TAF, and PegIFN- α 2a, refer to the respective prescribing information and Summary of Product Characteristics.

Risks specific for this study design are listed below:

- PegIFN- α 2a might increase the immunogenicity of JNJ-3989.
- Combination of PegIFN- α 2a with JNJ-3989 and JNJ-6379 might increase the risk of hematologic abnormalities and/or of bone marrow suppression.
- JNJ-6379 might increase tenofovir plasma concentrations.

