5.1.4. Baseline

In general, the baseline assessment is defined as the last observed non-missing measurement before the date and time of the first administration of any of study agents.

In case the first administration measurement time is missing, the first observed measurement on TP1 Day 1 will be used as the baseline measurement. If no observed measurement on Day 1, the last observed measurement before Day 1 will be used as the baseline assessment.

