5.1.5. Additional Reference Timepoint

An additional reference timepoint (RT) will be used for an additional analysis of selected efficacy endpoints for treatment period 2 and FU phase.

The RT for those analyses is defined as the last observed non-missing measurement before the first PegIFN- α 2a intake.

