Thyroid Function Tests	Thyroid Stimulating Hormone (TSH) Thyroxine (T4)

Clinical laboratory tests will be summarized using safety analysis set for chemistry, hematology, urinalysis and renal biomarkers panels.

Descriptive statistics (n, mean, SD, minimum, median, and maximum) will be calculated for each laboratory parameter for observed values and changes from baseline at each scheduled time point by analysis phase.

Shift tables will be provided summarizing the shift in laboratory values from baseline over time with respect to abnormality criteria (low, normal, high) for each laboratory parameter by analysis phase.

Descriptive statistics and graphical displays will be presented for all chemistry, hematology, and urinalysis laboratory tests at scheduled time points.

Change from baseline over time will be summarized for chemistry, hematology, urinalysis tests, and renal biomarkers.

Abnormality criteria (based on the criteria specified in the DAIDS Toxicity Grading Scale (see Clinical Protocol Appendix 9, DAIDS Table) will be applied to baseline and postbaseline values or in accordance with the normal ranges of the clinical laboratory if no gradings are available.

Postbaseline abnormalities will be compared with their corresponding baseline result:

- For toxicity grades, treatment emergent will be concluded if the postbaseline grade is worse than the baseline grade.
- For abnormalities based on normal range and/or criteria: If the postbaseline value is above the upper limit and the baseline value is below the upper limit (eg, Normal or Low), then the postbaseline abnormality will be considered TE. The same applies to the postbaseline value being below the lower limit with the baseline value being above the lower limit (eg, Normal or High).
- If the baseline value is missing, a postbaseline abnormality will always be considered as TE.

For each lab parameter, a worst-case analysis will be performed by using the worst abnormality and/or worst toxicity grade lab value and time point per participant. The worst toxicity case is the value associated to the highest toxicity grade and is derived per parameter and toxicity direction (hypo / hyper). Worst-case will be derived within each analysis phase, including unscheduled assessments. For abnormalities, in case the same participant has both abnormalities (low and high)

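### Period 2 and follow-up laboratory grades are judged only against Day 1, so an abnormality that predates PegIFN and persists is listed as treatment-emergent again; the effect is probably small and a supplementary table would net it out

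*Protocol*

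**What the plan says.** - **Baseline.** SAP 5.1.4 gives the usual rule: "the baseline assessment is defined as the last observed non-missing measurement before the date and time of the first administration of any of study agents". This is Day 1, and it is not reset when PegIFN starts at Week 12.
- **Emergence rule.** SAP 5.6.3.1: "For toxicity grades, treatment emergent will be concluded if the postbaseline grade is worse than the baseline grade".
- **Unit of counting.** Same section: "Worst-case will be derived within each analysis phase, including unscheduled assessments". Treatment-emergent worst grades are then tabulated by parameter and phase. SAP 5.6 presents safety for Period 1, Period 2, follow-up and overall.
- **Pre-PegIFN reference.** SAP 5.1.5 defines RT as the last non-missing value before the first PegIFN intake, for "an additional analysis of selected efficacy endpoints for treatment period 2 and FU phase". It is applied to HBsAg, HBeAg, HBV DNA, HBV RNA and HBcrAg, and nowhere in SAP 5.6.
- **The risk.** Protocol 2.3.2.2.3 lists, as specific to this design, that combining PegIFN with JNJ-3989 and JNJ-6379 "might increase the risk of hematologic abnormalities and/or of bone marrow suppression". Protocol 2.2.3.3 names bone marrow as a potential shared target organ.
- **Evidence without PegIFN.** Protocol 2.2.3.3 reports that, of 84 participants on JNJ-3989, "6 participants developed grade 1 platelet reduction with no general trend towards a continuous decline". Protocol 8.3.6.6 calls these cases transient and not clinically significant. For REEF-1, Protocol 2.2.3.3 says "overall around 5% of the participants experienced AEs or laboratory abnormalities related to hematologic abnormalities", and adds that these resolved while JNJ-3989 plus NA continued.

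**The concern.** There is no control arm, so each participant's own pre-PegIFN value is the natural internal reference for what happens once PegIFN is added. The SAP uses that reference for efficacy but not for safety.

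The Day 1 grade also discriminates little for hematology. Exclusion criterion A06.1 removes hemoglobin at or below 10.9 g/dL (men) or 10.4 g/dL (women), which is the top of DAIDS grade 1, and platelets at or below the lower limit of normal. Unless values move between screening and Day 1, participants start ungraded for hemoglobin. The same holds for platelets if the laboratory's lower limit is at least 125,000 cells/mm³ (an assumption). Worse than baseline then means almost any grade in the phase, whenever it began. At stake is how cleanly the Period 2 rate describes new or worsening abnormalities for a risk the protocol names.

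**Working it through.** **The plan's own figures.** The SAP gives no figure for laboratory emergence. Its one design calculation, the exact 90% intervals in Table 1, reproduces in all eight cells (for example 25/50: 0.376 to 0.624).

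**Step 1: does the rule recount?** The rule (worst grade in phase above reference grade) was applied to four invented platelet courses, in thousands per mm³. DAIDS grade 1 is 100 to <125 and grade 2 is 50 to <100. Day 1 is 160 in all four.

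| Course | Period 1 | RT | Period 2 | Follow-up | Emergent vs Day 1 (P1/P2/FU) | Emergent vs RT (P2/FU) |
|---|---|---|---|---|---|---|
| Persists | 140, 118, 115 | 115 | 114, 112, 116 | 118, 130 | yes/yes/yes | no/no |
| Resolves | 140, 118, 140 | 140 | 135, 130, 132 | 140, 150 | yes/no/no | no/no |
| Worsens | 140, 118, 115 | 115 | 80, 70, 75 | 110, 140 | yes/yes/yes | yes/no |
| New in P2 | 150, 150, 150 | 150 | 118, 110, 105 | 130, 150 | no/yes/no | yes/no |

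The two references differ in Period 2 only for the persisting course. Worsening or new onset counts under both.

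**Step 2: how many participants?** Inputs:
- q = 6/84 = 7.1% (exact 90% CI 3.2% to 13.6%), from Protocol 2.2.3.3.
- N = 50, taking all as PegIFN recipients.
- f = share of Period 1 cases still present, or recurring, in Period 2. Not in the documents; range 0 to 1.
- π = true rate of new or worsening grades in Period 2, assumed equal in carried-over and other participants. Not in the documents; range 0.1 to 0.5.

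Expected Period 1 onsets: 50 × 6/84 = 3.6.

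Period 2 rate against Day 1 = qf + (1 − qf)π. Against RT = π. Excess count = 50 × q × f × (1 − π):

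| f | π = 0.1 | 0.2 | 0.3 | 0.5 |
|---|---|---|---|---|
| 0 | 0 | 0 | 0 | 0 |
| 0.25 | 0.80 | 0.71 | 0.62 | 0.45 |
| 0.5 | 1.61 | 1.43 | 1.25 | 0.89 |
| 0.75 | 2.41 | 2.14 | 1.87 | 1.34 |
| 1 | 3.21 | 2.86 | 2.50 | 1.79 |

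The ceiling (f = 1, π = 0) is 3.6 of 50. As a rate, a true 10% would be tabulated as 10% at f = 0, 11.6% at f = 0.25, 13.2% at f = 0.5 and 16.4% at f = 1. By symmetry with the 0.90 row of Table 1, the 90% CI for 5/50 is 4.0% to 19.9%, so every one of these shifts lies inside it.

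**Step 3: neutrophils.** Criterion A25, re-checked at Week 12, lists a neutrophil count below 1,500 cells/mm³ (below 1,000 for Black or African American participants) among the PegIFN exclusions. DAIDS grade 1 is 800 to 1,000. A graded neutropenia present at Week 12 should therefore rarely be carried into PegIFN treatment. If it persists, it would mostly appear in Period 2 in someone not given PegIFN.

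**The case against.** The strongest reply is that the documents describe abnormalities that go away. Both accounts, transient in Protocol 8.3.6.6 and resolved in 2.2.3.3, point towards f near 0, where nothing is recounted. This stands as to size. Neither account gives a time to resolution, so resolution by Week 12 is likely but not established.

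Second, the Day 1 reference answers the stated objective, which is the safety of the whole regimen. This stands, and it is why the Day 1 tables should remain primary.

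Third, a reader might infer that the plan cannot show what changes after PegIFN starts. The documents do not support that. Changes from baseline are given at each visit, and the pre-PegIFN Week 12 sample is labelled separately. In the same participants, Week 24 mean change minus Week 12 mean change is the mean change from Week 12. Shift tables, plots and listings also reveal onset. Worst-grade counts, however, cannot be differenced in this way.

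A reader might also infer that Period 2 counts are being presented as PegIFN toxicity. The SAP nowhere says so, and Period 2 also includes participants who did not receive PegIFN.

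Nor should the roughly 5% from REEF-1 be multiplied by 50. It covers up to 48 weeks, pools adverse events with laboratory findings, and comes from a study with a JNJ-6379 arm. The 6/84 has limits too: it pools 25 to 400 mg at 7-, 14- or 28-day intervals (Protocol 4.3.1), and the documents do not claim that JNJ-3989 caused the cases.

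Finally, Protocol 9.4.3 refers safety analyses to the Master Protocol, which is not available here.

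**Conclusion.** The point holds as a gap in supplementary reporting. The rule relists an abnormality that began before PegIFN and persists or recurs, and no planned table removes it. For platelets the expected excess is between 0 and about 3.6 of 50 participants at the observed 6/84, probably near the lower end. The upper end requires every case to persist. The 6/84 rate is itself imprecise: its 90% CI of 3.2% to 13.6% corresponds to 1.6 to 6.8 onsets in 50. The cited cases were all grade 1, so persistence at that grade leaves grade 2 to 4 counts unchanged. Graded neutropenia is largely screened out at Week 12. The documents give no rate for hemoglobin.

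The stronger reading, that Period 2 laboratory rates are materially inflated or that PegIFN's contribution is unrecoverable, is not supported. The point concerns laboratory grades only, not adverse-event emergence.

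**What to change.** Keep the Day 1 tables as the main safety analysis. In SAP 5.6.3.1 add, for participants who receive PegIFN:

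1. Period 2 hematology and chemistry summaries of change from RT, with RT as defined in SAP 5.1.5. This is normally the predose Week 12 sample, or an earlier value if that one is missing.
2. Period 2 shift tables from RT grade.
3. A Period 2 table of worst grades that are worse than the RT grade.

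Add one follow-up table of grades worse than the last on-treatment grade, since RT does not handle an abnormality that starts in Period 2. Define that grade as the last Period 2 value (EOT2 in SAP Table 4). The on-treatment period in SAP 5.1.11 would not serve, because it runs on for as long as NA continues.

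Extend the scope sentence in SAP 5.1.5 to cover these tables.

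The cost is SAP wording and a few repeated tables. Week 12 hematology and chemistry are already scheduled and RT is already derived for efficacy.

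There is a small downside to state in the SAP. JNJ-3989 continues through Period 2, so the tables describe onset or worsening after PegIFN starts, not a pure PegIFN effect. An abnormality that would otherwise have resolved but fails to do so under PegIFN would not count as emergent in them. They must therefore be read beside the Day 1 tables.
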